5.7.4. Biological samples evaluation

5.7.4.1. Immunological read-outs

Blood samples will be collected for assessment of serology.

Table 10 Immunological read-outs

Blood sampling timepoint		study group	No. subjects	Component	Components priority rank
Type of contact and timepoint	Sampling timepoint				
Visit 2	Day 0	Coad group and RTS,S group	466	anti-CS	1
		Coad group and RTS,S group	466	anti-HBs	2
		Coad group and Control group	466	anti-catalase	3
Visit 4	Month 3	Coad group and Control group	466	anti-Me	1
		Coad group and Control group	466	anti-Ru	2
Visit 5	Month 4	Coad group and RTS,S group	466	anti-CS	1
		Coad group and RTS,S group	466	anti-HBs	5
		Coad group and Control group	466	anti-catalase	6
		Coad group and Control group	466	anti-Me	2
		Coad group and Control group	466	anti-Ru	3
		Coad group and Control group	466	anti-YF	4

In case of insufficient blood sample volume to perform assays for all antibodies, the samples will be analyzed according to priority ranking provided in [Table 10](#).

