APPENDIX A LABORATORY ASSAYS

Blood for analysis of humoral immune response will be obtained at timepoints listed in [Table 8](#). After centrifugation, serum samples should be kept at -20°C/-4°F until shipment.

Antibody titers against the CS repeat region

Antibody levels against *P. falciparum* CS-repeat region will be measured at CEVAC by a standard ELISA methodology using plate adsorbed recombinant R32LR antigen, as described by Clement [[Clement](#), 2012]. Anti-CS antibody titers will be determined relative to a standard reference antibody as a control according to standard operating procedures from the laboratory. The cut-off for the assay is 0.5 EU/ml. Results will be reported in EU/ml.

Antibody titers against the HB antigen

Anti-HBs antibody titers will be determined using commercially available CLIA kits ADVIA® Centaur anti-HBs2 manufactured by Siemens Healthcare. The cut-off for the assay is 6.2 mIU/ml. Results will be reported in mIU/ml.

Antibody titers against the catalase antigen

Anti-catalase antibody concentrations will be determined using in house ELISA. The cut-off for the assay is 65 ng/ml. Results will be reported in ng/ml.

Antibody titers against the measles antigen

Anti-measles antibody titers will be determined using commercially available ELISA kits Enzygnost™ manufactured by Dade Behring. The cut-off for the assay is 150 mIU/ml. Results will be reported in mIU/ml.

Antibody titers against the rubella antigen

Anti-rubella antibody titers will be determined using commercially available ELISA kits Enzygnost™ manufactured by Dade Behring. The cut-off for the assay is 4 IU/ml. Results will be reported in IU/ml.

Antibody titers against the YF antigen

Antibody levels against YF will be measured by a neutralization assay [[Osei-Kwasi](#), 2001]. The cut-off for the assay is 10 ED50. Results will be reported in ED50.

**SAFETY LABORATORY TESTING: CLS South Africa (Amended 09
August 2016)****Cerebrospinal fluid (CSF) for meningitis testing**

The recommended method for evaluation of meningitis will be through CSF analysis. The minimum acceptable volume for CSF should be 500 µl.

All CSF samples for suspected meningitis cases will be sent to CLS South Africa for CSF polymerase chain reaction (PCR) testing for selected common aetiological pathogens of meningitis as listed below.

- ***CSF: PCR testing***

	TEST
Bacteria	Haemophilus influenzae
	Streptococcus pneumoniae
	Neisseria meningitidis

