11.2.4. Immunogenicity

- For a given subject and given immunogenicity measurement, missing or non-evaluable measurements will not be replaced. Therefore, an analysis will exclude subjects with missing or non-evaluable measurements.
- The Geometric Mean Concentrations/Titres (GMC/Ts) calculations are performed by taking the anti-log of the mean of the log titre transformations (base 10). Antibody titres below the cut-off of the assay will be given an arbitrary value of half the cut-off of the assay for the purpose of GMT calculation. The cut-off value is defined by the laboratory before the analysis.
- A subject seropositive for anti-CS antibody will be a subject whose antibody titre will be greater than or equal to the cut-off value (anti-CS \geq 1.9 EU/ml).
- A subject seropositive for anti-HBs antibody will be a subject whose antibody titre will be greater than or equal to the cut-off value (anti-HBs \geq 6.2 mIU/ml).
- Seroprotection rate for anti-HBs antibody is defined as the percentage of subjects with antibody titres greater than or equal to 10 mIU/ml (anti-HBs \geq 10 mIU/ml).

- Seroconversion rate for anti-Me is defined as the percentage of children with an anti-Me pre-vaccination titre below 150 mIU/ml and a post-vaccination titre \geq 150 mIU/ml (i.e. the subject is seropositive post-vaccination and seronegative pre-vaccination for anti-Me).
- Seroconversion rate for anti-Ru is defined as the percentage of children with an anti-Ru pre-vaccination titre below 4 IU/ml and a post-vaccination titre \geq 4 IU/ml (i.e. the subject is seropositive post-vaccination and seronegative pre-vaccination for anti-Ru).
- Seroprotection rate for anti-Ru antibody is defined as the percentage of subjects with antibody titres greater than or equal to 10 IU/ml (anti-Ru \geq 10 IU/ml).
- A subject seropositive for anti-YF antibody will be a subject whose antibody titre will be greater than or equal to the cut-off value (anti-YF \geq 10 ED50).
- A subject seropositive for anti-catalase antibody will be a subject whose antibody concentration is greater than or equal to 65 ng/ml.
- The assay cut-off is the value under which there is no quantifiable result available. For an assay with a specific 'cut_off' , numerical immuno result is derived from a character field (rawres):
 - If rawres is 'NEG' or '-' or '(-)', numeric result= cutt_off/2,
 - if rawres is 'POS' or '+' or '(+)', numeric result = cut_off,

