 - if rawres is '< value' and value \leq cut_off, numeric result =cut_off/2,
 - if rawres is '< value' and value $>$ cut_off, numeric result =value,
 - if rawres is '> value' and value $<$ cut_off, numeric result =cut_off/2,
 - if rawres is '> value' and value \geq cut_off, numeric result =value,
 - if rawres is '<= value' or '>= value' and value $<$ cut_off, numeric result =cut_off/2,
 - if rawres is '<= value' or '>= value' and value \geq cut_off, numeric result =value,
 - if rawres is a value $<$ cut_off, numeric result = cut_off/2,
 - if rawres is a value \geq cut_off, numeric result = rawres,
 - if rawres is a value \geq cut_off, numeric result = rawres,
 - else numeric result is left blank.
 - All CI computed will be two-sided 95% CI.

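### SAP 11.2.4 counts a titre reported only as below a limit above the cut-off as seropositive for anti-Me, anti-Ru and anti-YF, which at Month 4 leans towards non-inferiority; the documents give no frequency for such results

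*SAP*

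**What the plan says.** SAP 11.2.4 explains that the "numerical immuno result is derived from a character field (rawres"), and defines the cut-off: "The assay cut-off is the value under which there is no quantifiable result available". A result of the form `< value` becomes half the cut-off when the value is at or below the cut-off. Above it, the instruction is "if rawres is '< value' and value $>$ cut_off, numeric result =value". A later branch treats `<= value` the same way once the value is at or above the cut-off.

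The same section sets the responder rule, for example: "A subject seropositive for anti-YF antibody will be a subject whose antibody titre will be greater than or equal to the cut-off value". Protocol Appendix A gives the assay cut-offs: for anti-Me, "The cut-off for the assay is 150 mIU/ml"; for anti-Ru, "The cut-off for the assay is 4 IU/ml"; for anti-YF, "The cut-off for the assay is 10 ED50". These are also the thresholds of the three secondary non-inferiority endpoints (SAP 4.2).

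Each comparison is Control minus Coad with a 10-point margin (SAP 6.4.1) and a Miettinen-Nurminen interval (SAP 6.4.2).

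**The concern.** A report such as anti-YF `< 20` ED50 says only that the titre is under 20. It may be 15, which is seropositive, or 6, which is not. The rule sets it to 20 and the child becomes a responder. The substituted number is the upper bound of what the laboratory reported, so the child is classed seropositive whatever the true titre.

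Nothing else in the plan catches this. The rule that missing or non-evaluable results are not replaced does not apply, because the recode has already supplied a number. Elimination code 2100 covers only results that are unavailable. The conditional second analysis on the Exposed Set (SAP 6.4.2) would use the same derived values. SAP section 9 lists only the anti-CS threshold change, and no sensitivity analysis addresses the rule.

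At stake are three secondary objectives with formal success criteria, each decided by a small number of non-responders. The geometric means also take the upper bound for any such result; that effect is not quantified here.

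**Working it through.** **Inputs.** N = 205 evaluable per group, two-sided alpha 0.05, reference rates 90% (anti-Me, anti-Ru) and 95% (anti-YF), all from Protocol 10.4 and Table 19; margin 10 points (SAP 6.4.1); Miettinen-Nurminen interval (SAP 6.4.2). The share of censored results is not in the documents and is assumed over a range.

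**1. The plan's own figures.** Exact binomial enumeration of the Miettinen-Nurminen criterion (upper limit below 10%), 205 per group and equal true rates, gives power 91.0% at 90% and 99.0% at 95%. Table 19 states 90% and 99%. The method reproduces the plan, and the power figures themselves are not in question.

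**2. Month 4 with equal reporting in both groups.** Let p be the true responder rate and q the share of true negatives reported as `< value` with the value above the cut-off. The recorded rate is

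p* = p + q(1 − p).

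The recorded difference is therefore

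pControl* − pCoad* = (1 − q)(pControl − pCoad) = (1 − q)D.

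At D = 10 points and q = 10%, the test sees 9 points against a 10-point margin.

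**3. Chance of a false non-inferiority conclusion at a true 10-point deficit:**

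| q (assumed) | Recorded difference | 90% vs 80% | 95% vs 85% |
|---|---|---|---|
| 0 | 10.0 | 2.5% | 2.4% |
| 5% | 9.5 | 3.4% | 3.5% |
| 10% | 9.0 | 4.7% | 5.0% |
| 20% | 8.0 | 8.9% | 10.1% |
| 30% | 7.0 | 16.0% | 19.1% |

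**4. Month 3 (anti-Me and anti-Ru only).** A recoded pre-vaccination result makes the child initially seropositive. That child then cannot count as a seroconverter, or leaves the initially seronegative denominator. This can move the difference either way. Anti-YF has no pre-vaccination sample, so only step 2 applies to it.

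**5. Does exclusion alone cure a borderline case?** Take Control 185/205 and recorded Coad 178/205, one of the 178 being a recoded result. Upper limits:

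- as recorded, 178/205: 9.76%, criterion met;
- that result excluded, 177/204: 9.85%, still met;
- that result counted seronegative, 177/205: 10.31%, not met.

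The pattern is the same at rates near the anti-YF reference with Control 195/205: 186/205 gives 9.71%, 185/204 gives 9.78% and 185/205 gives 10.28%. These cases place the affected child in Coad only. They show how close to the margin the handling matters, not what is expected.

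**The case against.** The strongest reply is that the trigger is undocumented. Each assay has one fixed cut-off, and nothing says a laboratory will report a limit above it. This stands: q may be zero. It does not make the rule right for the case it was written to cover.

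Four stronger readings are tempting, and the documents do not support them.

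- **Short serum produces such results.** Protocol 5.7.4.1 says: "In case of insufficient blood sample volume to perform assays for all antibodies, the samples will be analyzed according to priority ranking". That leaves lower-ranked assays without a result; it says nothing about higher starting dilutions. Amendment 1 also raised the blood volumes.
- **Coad would have more of them because its Month 4 sample serves six assays and Control's serves four.** The minimum draws in Protocol 5.6.12 sum to 1.2 + 0.6 + 0.6 + 0.6 = 3.0 ml for Coad, against 3.5 ml in Table 8. For Control they sum to 0.6 + 0.6 + 0.6 = 1.8 ml, against exactly 1.8 ml. Coad has the surplus, and the laboratory is blinded (Protocol 5.3).
- **A few recoded children would reverse the conclusion.** With Control 195/205 and true Coad 182/205 the upper limit is 11.95%. Recoding 4 of the 23 Coad negatives gives 186/205 and 9.71%, an apparent pass. That share is 17%; applied to Control's 10 negatives it is 1.7 children. Control 196/205 or 197/205 against 186/205 gives 10.15% or 10.58%, and the criterion still fails. The reversal depends on recoding one group only.
- **The rule always favours non-inferiority.** Step 4 shows this is not so for anti-Me and anti-Ru once Month 3 results are affected.

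Nor is any effect on the primary anti-CS conclusion shown.

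**Conclusion.** The rule is wrong as written: it turns an upper bound into evidence of seropositivity for all three secondary non-inferiority endpoints, and no other provision corrects it. At Month 4, with equal reporting in both groups, it biases the comparison towards non-inferiority. The inflation is modest at small shares (about 2.5% to about 3.5% at q = 5%, about 5% at q = 10%) and reaches 9 to 10% at q = 20%.

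These figures rest on an assumed q, equal q in both groups, 205 evaluable per group and no Month 3 recoding. The rule's wording is certain and its practical consequence is not. The case for changing it is that the text is incorrect and cheap to correct, not that a wrong conclusion has been shown to be likely.

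**What to change.** In SAP 11.2.4, replace the two branches. A `< value` result with the value above the cut-off, or a `<= value` result with the value at or above it, has indeterminate serostatus and is not seropositive. Then:

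1. Ask the laboratory for a repeat where serum remains. Amendment 1 raised volumes partly to allow repeat testing after invalid results.
2. If no repeat is possible, treat the result as non-evaluable under the existing missing-data rule.
3. Pre-specify a sensitivity analysis that counts every such Month 4 result as seronegative in both groups. This is essential, because exclusion alone can leave a borderline conclusion unchanged: in the 195 versus 182 example, dropping the four children gives 182/201 and an upper limit of 9.98%, still a pass. It is a bounding analysis rather than an estimate, since some of these children will be truly seropositive.
4. Report the number of such results by group, visit and assay. If there are none, the matter closes there.

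The cost is a few lines of SAP text, a small programming change and one short extra analysis. The downside is that a few results may become non-evaluable.

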11.2.5. Safety

- For a given subject and the analysis of solicited symptoms, missing or non-evaluable measurements will not be replaced. Therefore the analysis of the solicited symptoms based on the Exposed Set will include only vaccinated subjects for doses with documented safety data (i.e., symptom screen completed). More specifically the following rules will be used:
 - Subjects who documented the absence of a solicited symptom after one dose will be considered not having that symptom after that dose.
 - Subjects who documented the presence of a solicited symptom and fully or partially recorded daily measurement over the solicited period will be included in the summaries at that dose and classified according to their maximum observed daily recording over the solicited period.
 - Subjects who documented the presence of a solicited symptom after one dose without having recorded any daily measurement will be assigned to the lowest intensity category at that dose (i.e., 37.5°C for fever or grade 1 for other symptoms).
 - Doses without symptom sheets documented will be excluded.
- For analysis of unsolicited adverse events, such as serious adverse events or adverse events by primary MedDRA term, and for the analysis of concomitant medications, all vaccinated subjects (or receiving Vitamin A) will be considered. Subjects who did not report the event or the concomitant medication will be considered as subjects without the event or the concomitant medication respectively.
- The maximum intensity of local injection site redness/swelling will be coded as follows:

Grade	Redness/swelling
0	Absent
1	> 0 mm and < 5 mm
2	≥ 5 mm and ≤ 20 mm
3	> 20 mm

- For the analysis, temperatures will be coded as follows:

Grade	Temperature
0	< 37.5°C
1	≥ 37.5°C - ≤ 38.0°C
2	> 38.0°C - ≤ 39.0°C
3	> 39.0°C

Note that for all tables described in this section, the way the percentage of subjects will be derived will depend on the event analysed (see table below for details). As a result, the N value will differ from one table to another.

Event	N used for deriving % per subject for Vaccination phase	N used for deriving % per dose for Vaccination phase
Concomitant vaccination	All subjects with study vaccine administered	All study visits with study vaccine administered
Solicited general symptom	All subjects with at least one solicited general symptom documented as either present or absent (i.e., symptom screen completed)	All study visits with study vaccine administered and with at least one solicited general symptom documented as either present or absent (i.e., symptom screen completed)
Solicited local symptom	All subjects with at least one solicited local symptom documented as either present or absent (i.e., symptom screen completed)	All study visits with study vaccine administered and with at least one solicited local symptom documented as either present or absent (i.e., symptom screen completed)
Unsolicited symptom	All subjects with study vaccine administered	All study visits with study vaccine administered
Concomitant medication	All subjects with study vaccine administered	All study visits with study vaccine administered

Number of decimals displayed:

The following decimal description from the decision rules will be used for the demography, immunogenicity and safety/reactogenicity.

Display Table	Parameters	Number of decimal digits
Demographic characteristics	Mean, median, SD	1
Immunogenicity	GMT/C, including LL & UL of CI	1
Immunogenicity	Ratio of GMT, including LL & UL of CI	2
All summaries, Reactogenicity	% of count, including LL & UL of CI	1
All summaries	% of difference, including LL & UL of CI	2

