6.5. Analysis of safety

6.5.1. Analysis of safety planned in the protocol

The primary analysis will be based on the ES.

The percentage of subjects with at least one local AE (solicited and unsolicited), with at least one general AE (solicited and unsolicited) and with any AE during the solicited follow-up period [7 days post Dose 1, post Dose 2 and 14 days post Dose 3] will be tabulated with exact 95% CI after each vaccine dose and overall. The percentage of doses followed by at least one local AE (solicited and unsolicited), by at least one general AE (solicited and unsolicited) and by any AE will be tabulated for the overall vaccination course, with exact 95% CI. Similar tables will be generated for Grade 3 AEs and AEs considered as causally related to vaccination.

The percentage of subjects reporting each individual solicited local and general AE during the solicited follow-up period will be tabulated with exact 95% CI. The percentage of doses followed by each individual solicited local and general AE will be tabulated for each dose and for the overall vaccination course, with exact 95% CI. Similar tables will be generated for Grade 3 AEs, causal events and for fever, temperature in 0.5°C increments.

The proportion of subjects reporting an AE (unsolicited) until 30 days (Days 0-29) post each dose of RTS,S/AS01_E, classified by the Medical Dictionary for Regulatory Activities (MedDRA) preferred term level will be tabulated with exact 95% CI. The proportion of subjects reporting an AE (unsolicited) until 42 days (Days 0-41) after the administration of the YF vaccine and the combined measles and rubella vaccine (restricted to the Coad group and Control group), classified by the MedDRA preferred term level will be tabulated with exact 95% CI. Similar tables will be generated for Grade 3 AEs and AEs considered as causally related to vaccination.

The proportion of subjects reporting an SAE (all, fatal, related) occurring within 30 days (day of vaccination and 29 subsequent days) after each visit where a study product is potentially administered, classified by the MedDRA preferred term level will be tabulated with exact 95% CI.

The proportion of subjects reporting an SAE (all, fatal, related) from Day 0 to Month 4.5 and over the whole study duration (Day 0 to Month 33 for Coad and RTS,S groups and Month 36 for the Control group), classified by the MedDRA preferred term level will be tabulated with exact 95% CI.

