Overall/dose																
Drowsiness	All															
	Related															
	Grade 3															
	Grade 3*Related															
Irritability / fussiness	All															
	Related															
	Grade 3															
	Grade 3*Related															
Loss of appetite	All															
	Related															
	Grade 3															
	Grade 3*Related															
Temperature/ (Axillary) (°C)	All															
	Related															
	>39.0															
	>39.0*Related															
Measles/rube lla-like rash	All															
	Related															
	>39.0															
	>39.0*Related															

CONFIDENTIAL

200596 (MALARIA-073)
Statistical Analysis Plan Final

		Coad			RTS,S			Control								
		95 % CI			95 % CI			95 % CI								
Symptom	Type	N	n	%	LL	UL	N	n	%	LL	UL	N	n	%	LL	UL
Overall/subject																
Drowsiness	All															
	Related															
	Grade 3															
	Grade 3*Related															
Irritability / fussiness	All															
	Related															
	Grade 3															
	Grade 3*Related															
Loss of appetite	All															
	Related															
	Grade 3															
	Grade 3*Related															
Temperature/ (Axillary) (°C)	All															
	Related															
	>39.0															
	>39.0*Related															
Measles/rube-lla-like rash	All															
	Related															
	>39.0															
	>39.0*Related															

Coad =

RTS,S =

Control =

For each dose and overall/subject:

N= number of subjects with at least one administered dose

n/%= number/percentage of subjects reporting the symptom at least once

For Overall/dose:

N= number of administered doses

n/%= number/percentage of doses followed by at least one type of symptom

95%CI= Exact 95% confidence interval; LL = lower limit, UL = upper limit

Solicited symptoms are reported over 14 days post Dose 3

Template 35 Maximum temperature reported during the 7-day (Days 1-7) post-vaccination period (overall doses), per study group (Exposed Set)

Characteristics	Categories	Coad N =				RTS,S N =				Control N =			
		n	%	LL	UL	n	%	LL	UL	n	%	LL	UL
Maximum temperature	No fever												
	Unknown temperature												
	[37.5-38.0]												
	[38.1-38.5]												
	[38.6-39.0]												
	[39.1-39.5]												
	[39.6-40.0]												
	>40.0												

Coad =

RTS,S =

Control =

N = number of doses

n = number of doses in a given category

% = n / Number of doses with available results x 100

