Level 5: Not a case of generalized convulsive seizure

Within 14 days post Dose 3

Template 43 Incidence of seizures by diagnostic certainty level and history of fever within 7 days (1-7) post vaccination overall doses (Diagnostic certainty 1-5), per study group (Exposed Set)

		Coad N =				RTS,S N =				Control N =			
				95% CI				95% CI				95% CI	
Characteristics	Categories	n	n/1000	LL	UL	n	n/1000	LL	UL	n	n/1000	LL	UL
Level 1	History of fever												
	No history of fever												
Level 2	History of fever												
	No history of fever												
Level 3	History of fever												
	No history of fever												
Level 4 and 5	History of fever												
	No history of fever												

Coad =

RTS,S =

Control =

Total = Total

N = number of generalized convulsive seizures

n = number of generalized convulsive seizures in a given category

% = n / Number of generalized convulsive seizures with available results x 100

LL, UL for percentage = Exact 95% Lower and Upper confidence limits

Level 1: Witnessed sudden loss of consciousness AND generalized, tonic, clonic, tonic-clonic, or atonic motor manifestations

Level 2: History of unconsciousness AND generalized, tonic, clonic, tonic-clonic, or atonic motor manifestations
 Level 3: History of unconsciousness AND other generalized motor manifestations
 Level 4: Reported generalized convulsive seizure with insufficient evidence to meet the case definition
 Level 5: Not a case of generalized convulsive seizure
 Within 14 days post Dose 3

Template 44 Incidence of seizures by diagnostic certainty level and fever within 7 days (1-7) post vaccination overall doses (Diagnostic certainty 1-5), per study group (Exposed Set)

		Coad N =				RTS,S N =				Control N =			
				95% CI				95% CI				95% CI	
Characteristics	Categories	n	n/1000	LL	UL	n	n/1000	LL	UL	n	n/1000	LL	UL
Level 1	<38°C												
	≥38°C												
	Missing temperature												
Level 2	<38°C												
	≥38°C												
	Missing temperature												
Level 3	<38°C												
	≥38°C												
	Missing temperature												
Level 4 and 5	<38°C												
	≥38°C												
	Missing temperature												

Coad =

RTS,S =

Control =

Total = Total

N = number of generalized convulsive seizures

n = number of generalized convulsive seizures in a given category

% = n / Number of generalized convulsive seizures with available results x 100

LL, UL for percentage = Exact 95% Lower and Upper confidence limits

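### SAP 11.2.5 codes a solicited symptom with no recorded daily value as the mildest grade, so within each group the grade 3 and >39.0°C percentages can only fall or stay the same

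*SAP*

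**What the plan says.** SAP 11.2.5 opens its rules for solicited symptoms by stating that "missing or non-evaluable measurements will not be replaced". It then gives specific rules.

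- A child with the symptom present and some or all daily values is "classified according to their maximum observed daily recording over the solicited period".
- A child having "documented the presence of a solicited symptom after one dose without having recorded any daily measurement will be assigned to the lowest intensity category"; the value given for the dose is "37.5°C for fever or grade 1 for other symptoms".
- A dose with no symptom sheet is left out.

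The denominator table in the same section defines N for general symptoms as "All subjects with at least one solicited general symptom documented as either present or absent", with a parallel definition for local symptoms. A child with an assigned intensity therefore stays in N.

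The same section sets grade 3 at above 39.0°C for temperature and above 20 mm for redness and swelling. SAP 6.5.1 plans the tables that depend on these grades: "Similar tables will be generated for Grade 3 AEs, causal events and for fever, temperature in 0.5°C increments". In Annex 3, Template 35 (maximum temperature, overall doses) has a row labelled "Unknown temperature". Template 36 (the same display for one dose) shows no such row.

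The SAP plans neither a count of assigned intensities nor a sensitivity analysis of the rule.

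**The concern.** A child whose symptom is documented but never graded has an unknown severity. The rule turns that into the best possible value and counts the child in N as a known non-case for grade 3 or >39.0°C. For a safety summary this is not neutral, because any error from the rule lowers the severe-reaction percentage in that group.

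High fever is a result that readers will look at closely. Protocol 1.3.1 names febrile convulsion as an identified risk for both RTS,S/AS01_E and measles-containing vaccine. Protocol 1.2.3 extends solicited follow-up after Visit 4 to 14 days because of the timing of fever.

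There is also a problem of consistency. A programmer who follows the text codes such a fever as 37.5°C. One who follows Template 35 would place it in the unknown row. The two tables would differ.

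**Working it through.** The plan states no figure on this point, so there is nothing to reproduce. The check is a bound.

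**Inputs**
- N = 233 per group (Protocol 4.1), used as an illustration. The actual N is the number of children with a completed symptom screen.
- m = children with the symptom present and no daily value at that dose. The documents do not give it, so 0, 1, 2, 5 and 12 are assumed.
- x = children with a recorded grade 3 value. Not given; 7 is assumed.
- k = those of the m whose reaction was in truth grade 3, with 0 ≤ k ≤ m. Unknown.

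**Within a group**

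Reported = x/N. Counting the hidden cases = (x + k)/N. The shortfall is k/N, which lies between 0 and m/N and cannot be negative. An enumeration at N = 233 (x from 0 to 29, m from 0 to 19, every k) found no case in which the reported percentage was too high.

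With x = 7, the reported value is 7/233 = 3.0% (exact 95% CI 1.2 to 6.1) whatever m is:

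| m (assumed) | Largest shortfall, m/N (points) | Worst case, (7 + m)/233 |
|---|---|---|
| 0 | 0.00 | 3.0% |
| 1 | 0.43 | 3.4% |
| 2 | 0.86 | 3.9% |
| 5 | 2.15 | 5.2% |
| 12 | 5.15 | 8.2% |

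Any-grade incidence does not change, because the child still counts as having the symptom.

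**Between groups**

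Take equal reported percentages in Coad and RTS,S, and consider the true Coad minus RTS,S difference.
- 5 affected children in Coad only: 0 to +2.15 points.
- 5 in RTS,S only: −2.15 to 0 points.
- 5 in each: −2.15 to +2.15 points.

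The direction is not fixed.

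**Would dropping these children from N cure it?**

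Assume 100 symptomatic children among 233, of whom 10 are truly grade 3, and 5 symptomatic children without values. The true value is 10/233 = 4.29%.
- Missing values unrelated to severity (0.5 grade 3 cases lost on average): SAP rule 9.5/233 = 4.08%; dropping the 5 gives 9.5/228 = 4.17%, still 2.9% too low in relative terms.
- Severe cases three times as likely to lack values: the share of grade 3 cases lost is 3 × 0.05 / (0.9 + 3 × 0.1) = 12.5%, leaving 8.75. SAP rule 8.75/233 = 3.76%; dropping gives 8.75/228 = 3.84%, still 10.6% too low.

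Dropping removes only symptomatic children, the only ones who could be grade 3, so the bias remains.

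**Text against template**

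Under the rules, a fever with any recorded temperature takes its observed maximum, and a fever with none takes 37.5°C. No reported fever is left for the "Unknown temperature" row of Template 35.

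**The case against.** The strongest reply is that the rule will hardly ever apply. It needs a dose with the symptom reported and no value on any day. The study physician assesses the child on the day of vaccination, and staff then visit on Days 1 to 6, or Days 1 to 13 after Visit 4 (Protocol 5.6.14). Temperature is recorded daily (Protocol 8.1.3.2), and fever is itself defined by a temperature threshold (Protocol 8.2.3.2.1). This stands, and it is why the effect is probably small. It does not close every route. Protocol 8.1.3.1 lets redness on darkly pigmented skin be entered as uninterpretable, and the SAP has no separate rule for that entry.

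The templates are also weak evidence. Annex 3 says that they are illustrative, copied from another study and to be adapted. The sentence about not replacing values is followed by more specific rules, so the intended coding is clear. That explains the mismatch but does not remove it.

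A reader might infer more than the documents support:
- **That the sickest children are hidden.** A child admitted mid-period would normally have earlier daily values and fall under the rule for partial records. Hospitalisation makes the event an SAE (Protocol 8.1.2), and SAEs are analysed on all vaccinated subjects.
- **That a febrile-convulsion signal is masked.** Seizures within 30 days of Visits 2 and 3 and 42 days of Visit 4 are reported as SAEs (Protocol 8.1.5.2) and have their own tables. The "Missing temperature" row of Template 44 belongs to those seizure tables, so it does not contradict the diary-card rule.
- **That the rule favours co-administration.** The between-group effect has no fixed direction, and SAP 7 makes the safety comparisons descriptive.
- **That severe reactions will be understated by a large fraction.** Any such figure needs a missing rate that the documents do not give.

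**Conclusion.** The point holds as a minor one. Where the rule applies, an unknown severity is reported as mild, and the group's grade 3 and >39.0°C percentages can only fall or stay the same. The limit is m/N, or 0.43 percentage points per affected child at the planned 233 per group. That figure assumes a per-subject row with all 233 children in N. The number of affected children is unknown and may be zero, in which case the effect is nil. No success criterion depends on these tables.

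The wording conflict in SAP 11.2.5 and the mismatch with Template 35 exist whatever that number turns out to be, and should be reconciled.

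**What to change.** In SAP 11.2.5, delete the assignment to 37.5°C or grade 1. In its place:

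- Count a child with the symptom present and no daily value in the row for all intensities.
- Show the intensity as unknown, by group and dose. For fever, use the existing unknown row in Template 35 and add the same row to Template 36.
- Keep N as SAP 11.2.5 defines it. Do not remove these children from the grade 3 denominator.
- Add a worst-case sensitivity line that counts them as grade 3 or >39.0°C. The reported and worst-case lines then bracket what the missing intensities could hide.

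This also brings the rules into line with the bullet's opening statement. The cost is a short SAP edit, a small programming change, and one extra row and one extra line in the reactogenicity tables. If no child is affected, the row shows zero and the two lines agree.
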